## 17. Criteria for discontinuation and withdrawal from clinical studies

- 1) When the subject withdraws his/her consent to participate in the clinical trial
- 2) If the test cannot be continued due to a serious adverse reaction or sudden accident
- 3) If the test subject does not or is unable to comply with the visits and procedures specified in the plan.
- 4) If it is difficult to continue the test due to the manifestation of severe complications
- 5) If a test subject who does not meet the selection criteria participates in the test
- 6) If the test subject who meets the exclusion criteria participates in the test

In the event of dropout, the patient's records are kept confidential and are not used for study analysis. The patient is treated with known therapies even after opting out of the trial.

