## 16. Statistical analysis method

Statistical analysis will be performed using SPSS software. (SPSS version 22.0, IBM Corporation, Armonk, NY, USA),

Continuous variables (variables expressed as mean  $\pm$  standard deviations) will be compared using an independent t-test or Mann-Whitney U test, and categorical variables (including the presence of urinary retention and other adverse events) will be compared using a chi-squared test (or Fisher's exact test). Data are expressed as mean  $\pm$  standard deviation, median (25; 75 median), or number of patients (%). If the p-value is less than 0.05, it is considered to have statistical significance.

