#### **18. Evaluation criteria, evaluation methods, and reporting methods of safety including adverse events**

Since this study is conducted with standard treatment methods, there is no risk from clinical trials except for general side effects caused by general anesthesia and surgery.

The test method used in the study is recorded for causality and any adverse events, and the severity, severity, duration, and causal relationship with the test method are subsequently assessed. Treatment and consequences for adverse reactions are also recorded. Adverse reactions are evaluated by abnormal screening or additional tests and examinations as necessary, in addition to the planned screening and findings of the test during the test period, and immediate action is taken. Frequency, expression rate, list of each, severity, and causal relationship with test methods are presented, If necessary, report in the form of a graph.

1) Severe adverse reactions are classified into mild, severe abnormalities, and severe according to the following definition. Mild is normal, transient, and does not interfere with daily activities. Moderation causes some discomfort or interferes with daily activities. Severe illness is inability to perform daily activities. 2) Causality Causation is classified as 'not thought to be relevant', 'likely to be related', 'highly likely', 'obviously related', or 'difficult to ascertain relevance'.

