### **(2) Continuous safety monitoring plan of the target person**

In a clinical trial in patients undergoing general anesthesia and MAC anesthesia, researchers continuously monitor the patient's hemodynamic signs during the general anaesthesia and MAC sedation period. The duration of the double-blind examination is from the selection of the patient group to the primary endpoint 1 hour after surgery to the exit from the recovery room after confirming whether urinary retention occurs, and then up to 48 hours after surgery to check whether specific complications occur and determine whether the complications are relevant to the clinical trial. Details of the award are as follows: (relevant/irrelevant, start, end, last observation: recovered/recovering/not recovering/recovered but with sequelae/death/unknown)

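### Every dropout's records are excluded from analysis, even after treatment and after the primary outcome is known, which can bias the primary comparison and could remove serious reactions from the safety tables

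*Combined protocol and SAP*

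**What the plan says.** Section 17 of the combined protocol and SAP gives six reasons for discontinuation or withdrawal. Besides withdrawal of consent and failure to meet the selection criteria, they are:

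- "If the test cannot be continued due to a serious adverse reaction or sudden accident"
- a subject who "does not or is unable to comply with the visits and procedures specified in the plan"
- "If it is difficult to continue the test due to the manifestation of severe complications"
- "If the test subject who meets the exclusion criteria participates in the test"

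The list is followed by the only rule on dropout data in the document: "In the event of dropout, the patient's records are kept confidential and are not used for study analysis".

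Other sections assume that adverse events are counted. Section 16 says that "categorical variables (including the presence of urinary retention and other adverse events) will be compared using a chi-squared test (or Fisher's exact test". Section 18 says of adverse events: "Frequency, expression rate, list of each, severity, and causal relationship with test methods are presented". Section 22 (2) continues observation after recovery-room exit, "then up to 48 hours after surgery to check whether specific complications occur".

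Section 16 names tests but no analysis population and no rule for missing outcomes. Section 21, whose heading asks for the statistical analysis planning including any interim analysis, is answered as not applicable. Section 8 (suspension and elimination) drops patients whose surgery does not go ahead.

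**The concern.** Randomisation protects the comparison only if patients stay in the analysis whatever happens after treatment. Here, whether an observed outcome counts can depend on events after the reversal agent. The primary outcome is read at 1 hour (Section 15), while follow-up runs to 48 hours (Section 13, item 10), so a known primary outcome can be discarded later.

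Some of those later decisions may be unblinded. Section 13, item 6 keeps the patient and the anaesthetist blind only until recovery-room exit. The ineligibility reason has no time limit, and the last exclusion criterion in Section 8 is open researcher judgement. The text therefore permits a discretionary deletion when both allocation and outcome could be known.

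Two of the six reasons are themselves safety events. Applied literally, the rule removes from the adverse-event tables the patients whose events were serious enough to end participation, so the rates of those events could be understated.

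**Working it through.** **1. The texts side by side.** Section 17 excludes a dropout's records without qualification. Sections 16, 18 and 22 (2) compare, tabulate and follow adverse events. None of those three says that dropouts are kept. For a patient withdrawn because of a serious reaction the two instructions conflict, and nothing in the document says which prevails. This step needs no arithmetic.

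**2. The plan's own sample size.** Inputs from Section 7: 6/38 = 15.8% and 1/39 = 2.6%, allocation 1:1, two-sided 0.05, power 0.90, dropout about 10%. Exact Fisher power is 0.8987 at 100 per group and 0.9021 at 101. Then 101 × 1.10 = 111.1, rounded up to the stated 112. So the plan allows for about 112 × 0.10 ≈ 11 dropouts per group. Expected events are only 112 × 6/38 ≈ 18 and 112 × 1/39 ≈ 3, so the allowance is large relative to the event counts.

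**3. What selective loss would do (illustration only).** The documents give no dropout rate by outcome or by arm. Assumptions: loss L = 10% in the neostigmine arm, all after the drug; retention cases there lost r times as often as non-cases; no selective loss in the sugammadex arm; 101 analysed per arm. With p = 6/38:

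- non-case loss: dn = L / (p·r + 1 − p)
- case loss: de = r·dn
- observed rate = p(1 − de) / (1 − L)

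For r = 3: dn = 0.10 / (0.474 + 0.842) = 0.076, de = 0.228, and the observed rate is 0.158 × 0.772 / 0.90 = 13.5%. Power is taken against 1/39. Type I error takes both true rates as 15.8%. Both come from full enumeration.

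| r | Cases among that arm's dropouts | Observed rate | Fisher power | Fisher type I error | Chi-squared power | Chi-squared type I error |
|---|---|---|---|---|---|---|
| 1 | 16% | 15.8% | 0.90 | 3.3% | 0.94 | 5.1% |
| 2 | 27% | 14.5% | 0.85 | 3.9% | 0.90 | 5.9% |
| 3 | 36% | 13.5% | 0.80 | 5.1% | 0.86 | 7.5% |
| 4.8 | 47% | 12.3% | 0.71 | 8.0% | 0.79 | 11.2% |

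An extreme 20-fold ratio (79% of that arm's dropouts are cases) gives Fisher power 0.37 and type I error 26%. That is a bound, not an expectation.

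**4. How much the assumptions matter.**

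- Only half the loss is after the drug (L = 5%): r = 2, 3 and 4.8 give Fisher power 0.88, 0.86 and 0.83, and type I error 3.4%, 3.7% and 4.3%.
- The same r in both arms (L = 10%): Fisher power is 0.88, 0.86 and 0.84, and type I error stays at 3.3%, 3.2% and 3.1%.

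All of the type I inflation, and much of the power loss, therefore comes from loss that differs between arms.

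**5. What is possible within about 11 exclusions per arm.**

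- A true 18/112 against 3/112 (Fisher p = 0.0009) becomes 9/103 against 3/112 (p = 0.074) if nine neostigmine retention cases are removed.
- A null 10/112 in each arm becomes 10/112 against 2/104 (p = 0.035) if eight sugammadex cases are removed.
- If completers show 16/101 against 3/101, a difference of 12.9 points, the all-randomised difference could lie anywhere from 16/112 − 14/112 = 1.8 points to 27/112 − 3/112 = 21.4 points.

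These examples are chosen to be extreme.

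**The case against.** **Scope.** The exclusion sentence can be read narrowly. It sits beside a confidentiality promise, the next sentence speaks of patients opting out, and Section 10.2 uses dropping out for a voluntary choice. The consent text is not in our copy, so what patients were told about their data is unknown. But the sentence closes a list of six reasons, and Section 8 applies the same term to cancelled surgery. Even on the narrow reading, an already observed 1-hour outcome is deleted.

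**Route to bias.** The path to bias in the primary endpoint is short. The outcome is read 1 hour after recovery-room arrival, retention is managed within the protocol and is not a withdrawal reason, the 48-hour checks are planned in hospital, and some dropouts never receive the drug. All of this stands and makes a large bias less likely. The documents give no reason why retention cases should leave more often, or in one arm only, and step 4 shows how much rests on that.

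**Safety.** Sections 18 and 22 (2) could be held to prevail over a general sentence about analysis. That is a fair reading, but the document does not state it, so the conflict remains.

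**Blinding.** Section 22 (2) is loosely worded about when the double-blind period ends, and no section says who decides withdrawals. Unblinded deletion is therefore possible, not established.

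**Conclusion.** The concern holds and should be fixed before analysis. This is a stated rule that can give a wrong result, not merely a missing detail. It allows exclusion on post-treatment events and conflicts with the plan's own adverse-event reporting.

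The size and direction of any bias cannot be derived from the documents. Under the one-arm assumptions, a two- to threefold excess loss of retention cases has a modest effect: Fisher power 0.85 to 0.80 and type I error 3.9% to 5.1%. The effect is smaller if less of the loss follows the drug, and type I error does not rise if both arms select alike. The conclusion rests on the unqualified wording and the safety conflict, not on these figures.

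**What to change.** Replace the exclusion sentence in Section 17 with wording such as:

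*Withdrawal ends study procedures only. All randomised patients who received a reversal agent are analysed in their allocated arm, using all data collected up to withdrawal, unless the patient withdraws consent to data use. All treated patients are included in the safety tables.*

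Then:

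- State that randomised patients who never received a reversal agent, for example because surgery did not go ahead, are outside this set. Report their number and reasons by arm.
- Say explicitly that the set includes treated patients later found ineligible, and whether the safety tables go by allocated or received drug.
- Add a sensitivity analysis for a missing 1-hour outcome, counting missing as event and as non-event, by arm.
- Align Section 8 (suspension and elimination) and Sections 16, 17 and 18, and check Section 22 (2) against them.

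The cost is wording in those sections and one small analysis, with no extra patients or procedures. The sample size need not change: at the planned rates, Fisher power would be 93.2% if all 112 per group are analysed and 90.2% with 101. Whether the consent text needs a matching change cannot be judged from our copy.

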#### **18. Evaluation criteria, evaluation methods, and reporting methods of safety including adverse events**

Since this study is conducted with standard treatment methods, there is no risk from clinical trials except for general side effects caused by general anesthesia and surgery.

The test method used in the study is recorded for causality and any adverse events, and the severity, severity, duration, and causal relationship with the test method are subsequently assessed. Treatment and consequences for adverse reactions are also recorded. Adverse reactions are evaluated by abnormal screening or additional tests and examinations as necessary, in addition to the planned screening and findings of the test during the test period, and immediate action is taken. Frequency, expression rate, list of each, severity, and causal relationship with test methods are presented, If necessary, report in the form of a graph.

1) Severe adverse reactions are classified into mild, severe abnormalities, and severe according to the following definition. Mild is normal, transient, and does not interfere with daily activities. Moderation causes some discomfort or interferes with daily activities. Severe illness is inability to perform daily activities. 2) Causality Causation is classified as 'not thought to be relevant', 'likely to be related', 'highly likely', 'obviously related', or 'difficult to ascertain relevance'.

#### **19. Measures to protect personal information and maintain confidentiality of research data**

The subject's information completely removes the information that can identify the individual, and the document containing the inspector's record is stored in a locked place to prevent the leakage of information. Even after the end of the study, the subject's identity is accessible only to the participating researchers, and the subject's personal information is permanently destroyed three years after the end of the experiment. All researchers participating in this study are obliged to ensure the confidentiality of the research subjects.

**20. Management, storage, and disposal measures for the collection of human derivatives, etc.**  
Not applicable.

**21. Planning description of the statistical analysis of the study, including planning for interim analysis and the scope of early termination of the study if necessary**

Not applicable.

## **22. Continuous safety monitoring plan and data safety monitoring plan**

Since this study proceeds with the same setting as the actual clinical trial, except for the contents of blinding and group assignment, the additional risk that may arise from the study is minimal. Nevertheless, the principal investigator and the participating researcher entrusted by the principal investigator plan to monitor the safety of data and continuously monitor the safety of subjects during the experiment, under the supervision of the principal investigator.

### **(1) Monitor personnel**

Only the principal investigator and participating researchers authorized by the principal investigator are eligible, and the qualifications of the researchers are limited to those registered at Korea University College of Medicine or the Industry-Academia Cooperation Group. The monitor must be able to prove his or her qualifications with resumes, etc., and perform his or her duties in accordance with the clinical trial protocol, standard work instructions, monitoring plan, etc. The principal investigator is responsible for the monitoring and supervision of monitoring and for the quality and reliability of the data collected on the trial.

### **(2) Continuous safety monitoring plan of the target person**

In a clinical trial in patients undergoing general anesthesia and MAC anesthesia, researchers continuously monitor the patient's hemodynamic signs during the general anaesthesia and MAC sedation period. The duration of the double-blind examination is from the selection of the patient group to the primary endpoint 1 hour after surgery to the exit from the recovery room after confirming whether urinary retention occurs, and then up to 48 hours after surgery to check whether specific complications occur and determine whether the complications are relevant to the clinical trial. Details of the award are as follows: (relevant/irrelevant, start, end, last observation: recovered/recovering/not recovering/recovered but with sequelae/death/unknown)

### **(3) Data safety monitoring plan**

The principal investigator will check whether it is conducted and recorded in accordance with the clinical study protocol, standard work guidelines, clinical study practice standards and related regulations during the entire clinical trial cycle, and interim monitoring will be conducted in December 2023, final monitoring in December after the end of the trial in 2024, and a total of two sessions. Conduct evidence document verification such as case records, supporting documents, and other clinical trial-related documents for accuracy, completeness, and mutual agreement, and if the monitoring-related work is to be coordinated, risk assessment shall be carried out and the application shall be carefully examined according to the results.

### **(4) Risk assessment**

In adjusting and changing the type, scope, period, and scope of monitoring work, risk assessment is carried out and the results are documented. In this case, the procedure prescribed in the standard work manual shall be carried out including the following points.

1) Characteristics of clinical trial institutions identified through selection evaluation, etc.  
2) Procedures that have a significant impact on the quality, reliability, and completeness of clinical trial results;

fulfilment

3) Types of clinical trial data collected.

4) Clinical trial evaluation variables

5) Matters related to clinical trial design and blindfold maintenance

6) Characteristics of investigational drugs

7) In addition, the protection and safety of test subjects, the quality and reliability of clinical trial data, etc.

What's related

If the risk assessment is not carried out appropriately, the monitoring method, period, scope, procedure, etc. shall not be arbitrarily reduced or changed, such as the reduction of visit monitoring or the task of checking supporting documents, etc. for the clinical trial conducting institution, the test subject, the collected items, etc., and the monitoring method, cycle, scope, procedure, etc. according to the risk assessment result shall be reduced and if matters that significantly affect the quality and reliability of the clinical trial results and the safety of the test subjects are identified, the method before the reduction, Monitoring should be carried out according to the periodic procedure and scope.

### 23. Research Implementation Plan (Schedule)

Detailed development details	Detailed Timeline									
	2023. 1.	2	3-6	7-9	10-12	2024 . 1-3.	4-6	7-8	9-10	11-12.
Research Plan and Medical Research Review Committee Approval	■	■								
Recruitment and Conducting Research Procedures		■	■	■	■	■	■	■	■	
Data analysis and result reporting							■	■	■	■

